#### **6.1.8 Adverse Events Related to SMA**

The analysis of disease related events in Section 5.7.5 will present the overall incidence of events. To further explore the nature of these events the following categories of event will be presented. A blinded medical review prior to database lock will be conducted to ensure these proposed groupings are appropriate.

- Respiratory events: events that are coded into the SOC of respiratory, thoracic, and mediastinal disorders, either as their primary SOC or their secondary SOC
- Symptoms of gastric reflux: events identified by standardized MedDRA query (SMQ) for gastrointestinal nonspecific inflammations
- Athralgia and other issues related to joints: events identified by SMQ for arthritis to initially identify terms. The final set of terms will be refined by the medical review
- Scoliosis: events identified by the PT Scoliosis
- Contractures: events identified using the PTs: Extremity contractures, joint contracture, muscle contracture and tendinous contracture

#### **6.1.9 Presentations**

The following presentations will be shown:

- an overall summary showing, for each treatment group, the number and percentage of subjects with an adverse event, a moderate or severe event, a severe event, a possibly or related event, a related event, a serious event, an event that led to discontinuation of study drug, and an event that led to withdrawal from the study
- incidence by primary system organ class and preferred term
- incidence, by preferred term, in at least 5% of subjects in either treatment group
- incidence, by preferred term, of adverse events that occur with an incidence 5% or higher in any treated group (upon examining the actual data, different cut-off points may be used to examine the incidence of these adverse events if it is deemed more appropriate)

- incidence of mild, moderate and severe events by primary system organ class and preferred term
- incidence of severe events by primary system organ class and preferred term
- incidence of not related, unlikely to be related, possibly related, and related events by primary system organ class and preferred term
- incidence of drug-related events by primary system organ class and preferred term
- incidence of serious adverse events by primary system organ class and preferred term and a listing of serious adverse events
- incidence of death and a listing of each death
- incidence of events leading to discontinuation of study drug by primary system organ class and preferred term and a listing of such events
- incidence of events leading to withdrawal from the study by primary system organ class and preferred term and a listing of such events
- incidence of adverse events determined as following dosing/sham, by antibody status and events related to SMA (each category presented separately) by primary system organ class and preferred term and a listing of such events.

To avoid the potential for misleading interpretation of analysis of adverse events, no statistical testing will be performed.

## 6.2 Clinical laboratory data

Blood is to be drawn and urine collected for laboratory analysis at screening, and on Day 1 (pre-dose), 2, 29, 85, 169, 274 and 456. The following clinical laboratory parameters are to be assessed:

- Hematology: hemoglobin, hematocrit, red blood cell count, WBC count with differential both as absolute values and as a percentage (neutrophils, eosinophils, basophils, lymphocytes, and monocytes), and platelet count.
- Blood chemistry: liver function (total bilirubin, alkaline phosphatase, ALT/SGPT, AST/SGOT,) kidney function and electrolytes (BUN, creatinine, sodium, potassium, chloride), total protein, albumin, calcium, phosphorous, bicarbonate, glucose, cystatin C, and CPK.
- Urinalysis: specific gravity, pH, protein, glucose, ketones, bilirubin, blood, RBC, WBC, epithelial cells, bacteria, casts, and crystals.

As described below, laboratory data will be examined using an analysis of “shifts”. However further analyses may be undertaken to more fully characterize potential laboratory safety signals, such as assessment of timing, recovery, reversibility, association with adverse events, etc.

In the second approach, each subject’s laboratory values will be classified according to whether the test result is “low” (i.e., below the lower limit of normal [LLN]), “normal” (within the normal range), or “high” (i.e., above the upper limit of normal [ULN]). If a subject is missing a baseline value but had a post-baseline value, then the baseline assessment is labeled as “unknown”. Likewise, if a subject had a baseline value but had no post-baseline values, then the minimum and maximum are labeled as “unknown”. Post-baseline laboratory results are defined as any assessment taken after the first dose, including data collected from

local laboratories. The shifts (relative to the normal range) from baseline to the minimum and maximum post-baseline values will be presented. Should a treatment affect a laboratory parameter, that parameter could be affected at different times for different subjects.

Therefore, these analyses present the most extreme values for each subject. For many laboratory parameters, the effect could be in either direction, (i.e., an increase or a decrease), so both the maximum and minimum values have been analyzed. From these, the shifts (relative to the normal range) from baseline to low and high will be calculated. If a subject's value shifts, it can change from normal to either low or high, from low to normal or high, from high to normal or low, or from unknown to low, normal, or high. For each parameter, the incidence of shift to low will be summarized using the minimum post-baseline values. Shift to low includes subjects with a normal, high, or unknown baseline value and at least one post-baseline value of the given test. Similarly, the incidence of shift to high will be summarized using the maximum post-baseline values. Shift to high includes subjects with a low, normal, or unknown baseline value and at least one post-baseline value. All blood and urine samples will be used in the shift analyses.

Blood and urine samples for laboratory analysis are to be processed at a central laboratory. For many parameters, the laboratory has additional ranges, e.g., a notification to the site by telefacsimile that the subject's result is outside the normal range significantly enough to warrant notification, and/or a panic alert involving a telephone call made to the investigational site to notify them that the subject's result is outside of the normal range with potentially critical implications for the subject (see the table below). For shift tables of lab parameters, those additional categories will be combined with the conventional categories. Specifically,

- LT (Low – telefacsimile) and LP (Low panic) will be classified as L (Lower limit of normal)
- HT (How – telefacsimile) and HP (How panic) will be classified as H (Upper limit of normal)

For liver function tests, additional categories will be defined to present the baseline and post-baseline values as within the upper limit of normal,  $>1- <3 \times \text{ULN}$ ,  $\geq 3- <5 \times \text{ULN}$ ,  $\geq 5- <10 \times \text{ULN}$ ,  $\geq 10 - <20 \times \text{ULN}$ ,  $\geq 20 \times \text{ULN}$  for ALT/AST,  $>1- <2 \times \text{ULN}$ ,  $\geq 2 \times \text{ULN}$  for total bilirubin, and  $>1-1.5 \times \text{ULN}$  and  $\geq 1.5 \times \text{ULN}$  for alkaline phosphatase.

	LP	LT	L	H	HT	HP
HgB	X	X 	X	X	X 	X 
HCT	X	X 	X	X	X	
RBC		X	X	X		
WBC	X	X	X	X	X	X
Neutrophils ct	X 	X	X	X	X	
Lymphocytes ct		X 	X	X	X 	
Monocytes ct			X	X		
Eosinophils ct	-	-	-	X		
Basophils ct	-	-	-	X		
Neutrophils %			X	X		
Lymphocyte %			X	X		
Monocytes %			X	X		
Eosinophils %	-	-	-	X		
Basophils %	-	-	-	X		
Platelets	X	X	X	X	X	
Urea nitrogen			X	X	X	X
Bicarbonate		X	X 	X	X	
Creatinine			X	X	X	X
Glucose	X	X	X	X	X	X
Calcium	X	X	X	X	X	X
Phosphorus			X	X		
Total protein	X	X 	X	X		X 
Albumin			X	X		
CK			X	X	X	X
Sodium	X	X	X	X	X	X
Potassium	X	X	X	X	X	X
Chloride			X	X		
Cystatin C			X	X	X	
Total bilirubin			X	X	X	X
Alkaline phosphatase			X	X	X	X
ALT			X	X	X	X
AST			X	X	X	X

 6Y-150Y only;  Female: 0 to 3Y only, Male 0Y to 6Y only,  7M-2Y and 6Y-59Y females and 7M-59Y males only;  0Y to 6Y only;  4Y to 150Y only;  0Y to 4Y only.

-LLN is 0

LP: low panic

LT: Low – telefacsimile

L: lower limit of normal

H: upper limit of normal

HT: high – telefacsimile

HP: high - panic

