### ***10.6.2 Safety and Tolerability Analysis***

Safety analyses will be conducted in the Safety Set. Treatment duration and amount of Study Drug received will be summarized by treatment group.

All treatment-emergent adverse events and serious adverse events will be summarized for each treatment group using the MedDRA™ coding system, by system organ class, preferred term, relationship to Study Drug, and severity. Narratives of deaths, serious adverse events, including early withdrawals from Study Drug and from study due to adverse events, will also be provided.

Laboratory tests including chemistry panel, complete blood count with differential, etc., will be summarized by study visit for each treatment group. These safety variables will also be presented over time after Study Drug administration, as appropriate. Vital sign results will be presented similarly.

Physical and neurological examination findings and results from ECG will be listed for review. As appropriate, results will also be summarized descriptively for each treatment group. Concomitant medication usage for each subject will be listed for review.

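### Outside the liver tests, the SAP's laboratory shift tables fold alert and panic values into plain low or high, and no committed table counts panic values by arm

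*SAP*

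**What the plan says.** SAP 6.2 introduces its method with "As described below, laboratory data will be examined using an analysis of" shifts. Each result is classed as low, normal or high against the normal range. "The shifts (relative to the normal range) from baseline to the minimum and maximum post-baseline values will be presented", because a treatment effect may appear at different times in different children.

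Two incidence measures follow. For the low side: "Shift to low includes subjects with a normal, high, or unknown baseline value and at least one post-baseline value of the given test". For the high side: "Shift to high includes subjects with a low, normal, or unknown baseline value and at least one post-baseline value".

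The same section explains that the central laboratory has further ranges for many parameters. A telefacsimile alert (LT, HT) marks a result far enough outside the range to notify the site. A panic alert (LP, HP) prompts a telephone call because the result may be critical for the child. For the shift tables "those additional categories will be combined with the conventional categories": LT and LP become low, HT and HP become high. ALT, AST, total bilirubin and alkaline phosphatase are the exception and are also shown in graded multiples of the upper limit of normal. Further laboratory analyses are allowed but not promised.

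Protocol 10.6.2 says that laboratory tests "will be summarized by study visit for each treatment group", and adds presentation over time. SAP 6.2 contains no such summary. Its description of the shift classification calls it the second approach, and no first approach appears.

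**The concern.** The analysis takes each child's most extreme value and then discards how extreme it was. A child who falls from normal to panic-low platelets counts the same as one who falls just below the limit. A child who goes from slightly low to panic-low is not counted in the shift-to-low incidence at all.

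A drug effect on a laboratory parameter may show as a few large changes, or as worsening in children who were already abnormal. Both patterns are blurred or missed in the one laboratory table that SAP 6.2 sets out in detail. Safety is the trial's secondary objective, and the central laboratory already generates the flags that would show these patterns.

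**Working it through.** The plan states no figure to reproduce here. The check has three parts: a count from the SAP 6.2 flag table, a list of the transitions that the rules can register, and a comparison of the two documents.

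**1. Parameters affected**

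The table has 32 parameters, of which 21 have at least one alert or panic range.

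- Low-panic range (LP), 10 parameters: hemoglobin, hematocrit, WBC, neutrophil count, platelets, glucose, calcium, total protein, sodium, potassium.
- High-panic range (HP), 14 parameters, of which 4 are the graded liver tests. The other 10 are hemoglobin, WBC, urea nitrogen, creatinine, glucose, calcium, total protein, CK, sodium, potassium.
- In both lists, 7 parameters: hemoglobin, WBC, glucose, calcium, total protein, sodium, potassium.
- Distinct non-liver parameters with a panic range: 10 + 10 − 7 = **13**.
- Non-liver parameters with any alert or panic range: 21 − 4 = **17**. The extra four are RBC, lymphocyte count, bicarbonate and cystatin C, which have alert ranges only.

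**2. Transitions registered**

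Order the levels LP, LT, L, normal, H, HT, HP. Downward moves that end in a low level are:

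| Ends in | Possible starting levels | Moves |
|---|---|---|
| L | normal, H, HT, HP | 4 |
| LT | L, normal, H, HT, HP | 5 |
| LP | LT, L, normal, H, HT, HP | 6 |
| Total | | 15 |

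After the merge, and with the rule that the baseline must not be low:

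- Counted as a shift to low: 4 non-low starting levels × 3 low end levels = 12. The three end levels cannot be told apart.
- Not counted: L to LT, L to LP and LT to LP, so 15 − 12 = 3.

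The high side mirrors this. The omission works by direction: a child low at baseline leaves the shift-to-low incidence but stays in shift-to-high.

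**3. The two documents side by side**

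- Protocol 10.6.2 asks for laboratory results by visit and arm, and says vital signs will be presented similarly.
- SAP 6.4.1 and 6.4.2 do this for vital signs, with actual values and changes at each time point. SAP 6.2 does not do it for laboratory tests.
- Protocol 10.6 leaves the detailed methodology to the SAP, so a table missing from the SAP has no specification elsewhere.
- The SAP already counts children beyond thresholds for corrected QT (6.3.2) and for liver tests (6.2). A count of panic values would follow the same practice.

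**The case against.** A reader might infer that the worst laboratory deterioration cannot be seen in any comparison of the arms. The documents do not support that.

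- Protocol 10.6.2 still requires by-visit summaries by arm. SAP 3 says summary statistics will be given throughout and that continuous summaries generally include minimum and maximum.
- Clinically significant abnormalities may be recorded as adverse events (protocol 9.5.1), which are tabulated by arm and severity.
- Patient listings include the laboratory transfers (protocol 10.6), and the DSMB reviews unblinded safety data.
- Every panic value still counts as low or high in the shift from baseline to the post-baseline minimum or maximum, and that presentation states no baseline exclusion.

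Nor can one infer that the sponsor chose to drop the by-visit summary. Where the SAP departs from the protocol on the interim alpha (5.1) and on milestone imputation (5.3), it says so. It announces no departure for laboratory data, so the missing first approach may be a drafting slip.

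It would also go too far to replace the three-level table with a seven-level one. Several flags depend on age or sex: hemoglobin LT, HT and HP exist only from age 6, and lymphocyte LT and HT only up to age 6. In a trial of ages 2 to 12, such a table would mix children for whom a level exists with children for whom it does not. Local-laboratory results also enter the analysis, and nothing shows that they carry the central flags. The three-level table is a defensible choice.

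All of this stands, and it limits the claim. It does not supply the missing count. A minimum or maximum shows one child per arm and visit, not how many reached panic level. Listings are not an arm comparison. The adverse event route depends on investigator judgement and prefers a diagnosis to a laboratory value. The optional further analyses are not a commitment.

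**Conclusion.** The point holds as a minor gap in safety presentation. For 13 non-liver parameters with a panic range, no committed table shows how many children per arm reached a panic value. For 17 non-liver parameters the alert grading is lost in the shift tables, and same-direction worsening from an abnormal baseline is not counted in the incidence. SAP 6.2 also fails to specify the by-visit summary that the protocol requires.

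The counts rest on the flag table as it reads in SAP 6.2. How many children would be affected cannot be stated, because the documents give no frequency of abnormal baseline values. Exclusion criterion 11 removes children whose clinically significant hematology or chemistry abnormalities make them unsuitable, so seriously abnormal baselines should be less common, though milder ones can be enrolled. The primary inference is untouched.

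**What to change.** 1. Keep the low/normal/high shift table.
2. Add a descriptive table, by arm and parameter, of children with any post-baseline LT, LP, HT or HP value, split by baseline category so that low to panic-low is visible. Use as denominator only children whose age and sex have that flag defined.
3. State how local-laboratory results without central flags are handled in that table.
4. Supply the missing first approach in SAP 6.2: values and change from baseline by scheduled visit and arm, as protocol 10.6.2 requires.

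The cost is some extra tables and a short rule for age- or sex-specific flags and local-laboratory values. The table is descriptive, needs no new data collection and spends no alpha.

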### 6.3 ECGs

ECGs are to be recorded at screening, and on Days 2, 29, 92 and 456 and will be quantified prior to the final database lock at a central reading laboratory. ECG qualitative results include an overall interpretation of ‘normal’, ‘abnormal but not clinically significant’ or ‘abnormal and clinically significant’. ECG quantitative parameters include heart rate, PR interval, QRS duration, uncorrected QT interval, and corrected QT interval.

ECGs will be analyzed using two approaches.

#### 6.3.1 Qualitative analysis

Incidence tables will summarize both the number and percentage of subjects with an abnormal, clinically relevant baseline ECG and the number and percentage of subjects with

abnormal, clinically relevant worsening, defined as a post-baseline ECG interpreted as abnormal and clinically relevant, with a comparison with baseline value of deteriorated, not available, not required, or missing. The incidence of clinically relevant worsening will be summarized at any time post-baseline and by visit post-baseline. In addition, a summary of abnormality types and findings within abnormality types will be provided for subjects with an abnormal, clinically relevant baseline ECG and for subjects with abnormal, clinically relevant worsening.

### **6.3.2 ECG outliers**

Outlier analyses will be performed for the corrected Fridericia QT interval. This will include summaries of the number and percentage of subjects with a post-baseline corrected QT interval greater than certain threshold values (e.g., >450 msec, >480 msec, and >500 msec) and the number and percentage of subjects with an increase from baseline in corrected QT interval in various categories (e.g., >30 msec and >60 msec). These summaries will be performed on an overall basis, as well as separately for subjects whose baseline corrected QT intervals are normal ( $\leq$  450 msec) and elevated ( $>$ 450 msec).

## **6.4 Vital signs**

Vital signs are to be measured at screening, pre-dosing and at 1, 2, 4, 6, and 20-24 hours post-dosing on dosing days (Days 1, 29, 85 and 274). Additionally, assessments are made on Days 92, 169, 365 and 456. At each of these times, temperature, heart rate, respiratory rate, systolic and diastolic blood pressure will be measured.

If multiple evaluations are on the same visit day and visit time, then the mean of these evaluations will be selected for inclusion in the analysis.

The analysis of vital signs will be approached in two ways.

### **6.4.1 Acute effects after dosing**

On each dosing day, the change in each vital sign from pre-dosing on that day to post-dosing (i.e., from pre-dosing to 1 hour post-dosing, to 2 hours post-dosing, etc.) will be calculated. Summaries of actual values and change from pre-dosing for each dosing day will be presented.

### **6.4.2 Chronic effects**

To examine for possible chronic effects, the change from baseline (the pre-dosing value on Day 1) to the pre-dosing value on later dosing days and to Days 92, 169, 365 and 456 will be determined. Summaries of actual values and change from baseline to each of these time points will be presented.

## **6.5 Neurological examinations**

Neurological examinations include assessment of mental status, level of consciousness, cranial nerves, reflexes, motor system, coordination/cerebellar function and sensation – temperature and vibration. These are to be assessed at screening, pre-dosing and at 5 and 20-24 hours post-dosing on dosing days (Days 1, 29, 85 and 274) and on Days 92, 169, 365 and 456.

The result collected for the majority of the tests is ‘normal’ or ‘abnormal’, however the assessment of sensations is reported as ‘present’ or ‘absent’ and the assessment of reflexes is captured on an ordinal scale. For each test it is recorded if secondary to SMA.

#### **6.5.1 Acute effects after dosing**

On each dosing day, the shifts from pre-dosing assessment on that day to post-dosing (i.e., from pre-dosing to 5 hours post-dosing, to 24 hours post-dosing) will be determined.

For each test and post dosing time point, the number and proportion of subjects who moved from ‘Normal’ to ‘Abnormal’ will be presented, for sensations the number and proportion who move from ‘Present’ to ‘Absent’ will be presented. For the assessment of reflexes decreases (from pre-dosing 1 to post doing 0, 2 to 1 etc) will be presented. Only changes not deemed secondary to SMA will be presented.

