### **4.4 Unblinding of Treatment Assignment**

The Sponsor, parents, and key study site personnel will be blinded to subjects' treatment assignment throughout the study. The DSMB may be unblinded as described in the DSMB charter. Representatives from the Sponsor may be unblinded at the interim analysis as described in the unblinding plan. Those Sponsor representatives will no longer be involved in the conduct of the study after they have been unblinded.

If a subject has experienced an SAE (as defined in [Section 9.3.3](#)), and/or when knowledge of the treatment assignment will impact the clinical management of the subject, the Investigator will

have the ability to unblind the treatment assignment for that subject using the IXRS. However, prior to unblinding, the Investigator should attempt to contact the blinded Medical Monitor to discuss the emergency. The Sponsor or designee will be informed of the unblinding of a subject within 24 hours. Every reasonable attempt should be made to complete the Study Day 456 early termination procedures and observations (see [Appendix A](#)) prior to unblinding, as knowledge of the subject's treatment assignment could influence subsequent assessments. The Investigator must document the reasons for unblinding in the subject's source documents. The Investigator is strongly advised not to divulge the subject's treatment assignment to any individual not directly involved in managing the medical emergency, nor to personnel involved with the analysis and conduct of the study. In cases where there are ethical reasons to have a subject remain on study whose treatment assignment is unblinded for safety reasons, the Site Investigator must obtain specific approval from the Sponsor and the Medical Monitor for the subject to continue in the study.

In addition, all suspected unexpected serious adverse reactions (SUSARs) will be unblinded by the Sponsor's Drug Safety and Quality Assurance personnel for the purpose of regulatory reporting ([Section 9.2](#)).

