#### **6.5.2 Chronic effects**

To examine for possible chronic effects, changes from baseline (the pre-dosing value on Day 1) to the pre-dosing value on later dosing days and to Day 92, 169, 365 and 456 will be determined. Summaries will be presented in a similar manner to that described for the acute effects.

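### The SAP's neurological shift tables omit changes attributed to SMA and all reflex increases, so drug-related neurological change could be diluted or lost in them

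*SAP*

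**What the plan says.** SAP 6.5 schedules neurological examinations at screening, before each of the four procedures, at 5 and 20–24 hours after each, and on Days 92, 169, 365 and 456. Most tests are scored normal or abnormal, sensation is present or absent, and reflexes are graded on an ordinal scale. On attribution it says "For each test it is recorded if secondary to SMA". It does not say who makes that judgement.

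For the acute tables, SAP 6.5.1 states that "the number and proportion of subjects who moved from ‘Normal’ to ‘Abnormal’ will be presented", with the matching present-to-absent count for sensation. It continues: "For the assessment of reflexes decreases (from pre-dosing 1 to post doing 0, 2 to 1 etc) will be presented". The paragraph then closes with "Only changes not deemed secondary to SMA will be presented". That sentence is not tied to any one test, so I read it as governing all of them. For the chronic tables, SAP 6.5.2 says "Summaries will be presented in a similar manner to that described for the acute effects".

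Protocol 10.6.2 is broader. It says "Physical and neurological examination findings and results from ECG will be listed for review", and its next sentence provides for descriptive summaries by treatment group where suitable. It mentions neither attribution nor direction of change. Protocol 4.4 states that "key study site personnel will be blinded" to treatment assignment.

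**The concern.** The drug is injected intrathecally, and neurological examinations are a named safety endpoint. The children have a disease of the motor neurons and, under inclusion criterion 5, have never walked independently. Three features of the tables reduce what they can show in this population.

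- **Attribution.** New weakness or reflex loss is the kind of finding most readily ascribed to SMA. Once ascribed, it leaves the table.
- **Starting state.** A child whose motor examination is abnormal before dosing cannot register a normal-to-abnormal shift, and a reflex already graded 0 cannot decrease.
- **Direction.** A reflex increase is not tabulated at all.

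The trial has a randomised sham arm. Disease-related change should occur in both arms, so an excess on drug would be visible without any judgement of cause. At stake is the sensitivity of the planned neurological tables to harm.

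**Working it through.** The documents give no rate of neurological worsening and no share attributed to SMA, so there is no planned figure to reproduce. The check has two parts.

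**1. Effect of the attribution filter (illustration).**

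Inputs: 84 active and 42 sham subjects (SAP 5.1). Worsening rates of 20% active and 5% sham are assumed. The share f of worsenings deemed secondary to SMA is unknown and varied. It is taken as equal in both arms because key site staff are blinded.

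- Tabulated count = n × rate × (1 − f)
- Tabulated difference = (0.20 − 0.05) × (1 − f)
- Tabulated risk ratio = [0.20 × (1 − f)] / [0.05 × (1 − f)] = 4.0 for any f below 100%

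| f | Active, of 84 | Sham, of 42 | Difference (points) |
|---|---|---|---|
| 0% | 16.8 | 2.1 | 15.0 |
| 25% | 12.6 | 1.6 | 11.3 |
| 50% | 8.4 | 1.1 | 7.5 |
| 75% | 4.2 | 0.5 | 3.8 |
| 90% | 1.7 | 0.2 | 1.5 |

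At f = 90% the tabulated active rate is 0.20 × 0.10 = 2%. The chance that no active subject appears is then (1 − 0.02)^84 = 18%. Only f = 100% removes the signal entirely.

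Other assumed rates follow the same pattern. For 15% versus 5%, the difference is 10.0 points unfiltered, 5.0 at f = 50% and 1.0 at f = 90%. For 30% versus 10%, it is 20.0, 10.0 and 2.0.

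**2. Whether other planned outputs fill the gap.**

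- *Adverse events.* Protocol 9.3.1 defines these regardless of cause, SAP 6.1 tabulates all treatment-emergent events by arm, and SAP 6.1.6 gives windows of 0–6, 6–24 and 24–72 hours after each procedure. However, the opening of SAP section 6 requires worsening or new findings to be reported as adverse events for physical examinations only. Neurological examinations are not named, so a subclinical shift need not become an event.
- *Disease-related event rates* (SAP 5.7.5). These are compared between arms, but they draw on the same adverse event records.
- *HFMSE.* This is compared by arm with no attribution filter, but the first post-baseline assessment is Day 92. It cannot see a change at 5 or 24 hours, and it is a motor function scale, not a reflex or sensory examination.
- *Listings.* These hold all findings but do not compare arms.

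Elsewhere the SAP does not restrict in this way. Laboratory shifts use both the minimum and the maximum because an effect may go either way (SAP 6.2). All adverse events are tabulated, with drug-related events as a further table (SAP 6.1.3 and 6.1.9). Vital sign changes carry no attribution filter (SAP 6.4).

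**The case against.** The strongest reply is that the filter touches one set of descriptive tables. A reader might infer that neurological toxicity would be removed from the randomised comparison altogether. The documents do not support that: changes not attributed to SMA are still shown, the adverse event, disease-related event and HFMSE outputs do not depend on this flag, and the DSMB reviews unblinded safety data (SAP section 2). Nor is it right that the protocol offers listings alone, since Protocol 10.6.2 also provides for by-arm summaries.

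A second inference would be that the filter biases the result towards no effect. That is not shown. Applied alike in both arms by blinded raters, it leaves the risk ratio unchanged, and distortion in favour of one arm would need some failure of the blind. It is also an inference that the investigator supplies the flag.

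Third, a change within a day of dosing is the least natural one to blame on a chronic disease, so f may be low in the acute tables. This is fair. The attribution argument is stronger for SAP 6.5.2 than for 6.5.1.

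Fourth, dropping the filter does not recover children who were already abnormal before dosing, because an unfiltered normal-to-abnormal count misses them too. This also stands. Denominators make that limit visible but do not remove it.

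These points narrow the concern without answering it. The by-arm summary in the protocol is discretionary and the SAP has implemented it narrowly. The other outputs leave acute and subclinical motor and reflex change without an unfiltered comparison.

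**Conclusion.** The concern holds as a loss of sensitivity in the neurological shift tables. Both restrictions are in SAP 6.5.1, carry over to 6.5.2, and are absent from Protocol 10.6.2. Drug-related motor or reflex change could be diluted or lost there, and no planned table shows reflex increases by arm.

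The size is unknown because f is unknown. The absolute difference is multiplied by 1 − f, under the assumption of equal attribution in both arms. How many children cannot register a shift is also unknown, since the documents give no baseline rate of abnormal examinations. That motor and reflex worsening is readily ascribed to SMA is a judgement from the nature of the disease, not a figure in the plan. The documents do not support a claim of bias in the relative comparison, or of complete loss of the signal from the trial. The change is still worth making because it adds sensitivity to harm at almost no cost.

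**What to change.** In SAP 6.5.1 and 6.5.2:

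1. Make the main table all neurological shifts by treatment arm and time point, whatever the attribution. SAP 6.5.1 does not itself say the counts are split by arm, so state it.
2. Keep the subset not deemed secondary to SMA as a supplementary table, and say which visit's flag decides whether a change belongs to it.
3. For reflexes, show increases as well as decreases.
4. For the binary tests, give the number normal (or, for sensation, present) at pre-dose or baseline as the denominator, so that a small at-risk group can be seen.

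This brings the SAP into line with Protocol 10.6.2. It needs SAP wording and a few more descriptive tables from data already collected, with no new assessments. The price is that more disease-related background shifts will appear in both arms, and the reader will have to compare the arms.
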